10.1.2. Secondary estimands

• For a given endpoint, the secondary estimand will be the population average treatment effect on the change from baseline at a given time assessment (i.e., on Day 16, Day 45 or Day 90) of nirmatrelvir/ritonavir compared to placebo/ritonavir. Measurements after discontinuation of study intervention will be censored and treated as missing data. Missing data due to censoring, study withdrawal or other reasons (e.g., laboratory failure) will have data imputed based on a missing at random (MAR) assumption. Participants with inadequate compliance will have their values used as-is in the analysis. The

 Version No:
 2.0 Final

 Date:
 10 March 2023

 EudraCT No:
 2022-003855-32

population-based treatment effect will be the difference in the mean change from baseline in nirmatrelvir/ritonavir arm compared to placebo/ritonavir.

10.2. Analysis populations

Participant Analysis Set	Description
Full Analysis Set (FAS)	All participants completing randomization
Safety Analysis Set (SAS)	All participants randomly assigned to study intervention and who take at least 2 doses of study intervention. Participants will be analyzed according to the study intervention they received.
Modified Intent -To-Treat (mITT)	All participants randomly assigned to study intervention who complete 25 dosings up to Day16. Participants will be analyzed according to the study intervention to which they were randomized.
Full Completers (FC)	All participants in the set without major protocol violations who completed at least 25 dosings and were assessed at Day16, Day45 and Day90

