 2.0 Final

 Date:
 10 March 2023

 EudraCT No:
 2022-003855-32

Ritonavir in the comparative arm is chosen, as ritonavir may cause adverse effects such as nausea and may thus make it unblind to both study participant and study team. Possible interactions will be considered on an individual level for each patient.

Active standing test: An active standing test will be performed at the baseline visit and on Day 45 and 90 of follow-up. Heart rate (ECG) and blood pressure (Arm-cuff) will be measured after 10 minutes bed rest and for ten minutes standing as well as 5 minutes bed rest after return to supine position. ECG and blood pressure measurements are non-invasive and do not imply any risk for the study subjects. The orthostatic challenge itself is not associated with any foreseeable risk for bodily harm but may be uncomfortable and may produce new or worsening symptoms including lightheadedness, dyspnea, chest pain, syncope, headache, blurred vision, and palpitations. To mitigate the risk for serious symptoms the test will be performed by staff trained in active standing tests and study subjects may abort the test and return to supine position if he or she chooses to.

Endothelial function test: Endothelial function will be measured at baseline and day 45 during follow-up using an EndoPAT® device (Itamar medical). The procedure is non-invasive and takes approximately 20 minutes. After a stabilization period an arm cuff will be inflated to supra systolic pressure for five minutes, The cuff is then deflated, and endothelial function is measured as reactive hyperemia index in the index finger. The procedure is not associated with any foreseeable risk for bodily harm. However, it may be uncomfortable and in rare cases even painful. The procedure will be performed by staff trained in the procedure and the study-subject can opt to abort the measurement at any time.

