^d Only required if a participant does not have results of a positive SARS-CoV-2 test that was obtained within 5 days prior randomization. If the test is positive, subject can be re-screened at a later stage.

e At baseline, an NP swab will be collected by the investigational site staff to confirm SARS-CoV-2 infection by RT-PCR. This test will not be used to determine study eligibility. Subsequent NP or nasal swabs will be collected on Days 1, 16 and 45.

The investigator will capture contact information for at least 2 individuals who the site can contact if the participant is unable to be reached after multiple attempts.

⁹ Includes grip strength, 6-minute walk test, and accelerometer. At Screening only accelerometer assessment will be initiated.

^h Only patients diagnosed with POTS.

Apply Days 16 and 45 for up to 5 days registration.

PROs will be administered for the option to complete at home prior to next visit.

^k Laboratory tests at Days 45 and 90 are required only if clinically relevant abnormal laboratory values were present from a sample drawn at the previous study visit when laboratory assessments were performed.

SAE (s) are reported from the time point ICF is signed until Day 90 visit. AE's are reported from first intake of study treatment until Day 90 visit.

^m Potential for long-term clinical follow-up at 6 and 12 months through EMR and national registries

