5.2.3. Baseline - Day -1

A patient study diary in paper format will be provided for the study participants where intake of investigational product is to be recorded.

Patients will be instructed who to contact in case of study related emergencies and will be provided with a study specific patient card.

The questionnaires will be distributed to fill in at the site, but if too burdensome, the option to complete at home will be given.

The option to distribute questionnaires to fill in prior to next visit will be given, and the forms will be supplied.

Patients will be informed to pay attention to changes in health during the study, to be able to report adverse events on their next visit.

5.2.4. Start of Treatment - Day 1

Patients will start treatment and register intake of investigational product. Patients will be instructed to keep empty blisters and bottles, and bring together with unused IMP, to the clinic on Day 16 visit.

Adverse event reporting starts from intake of the first dose of investigational product.

5.2.5. Visit - Day 16

Remaining IMP as well as empty blisters and bottles are collected for drug accountability. The patient study diary will be collected and reviewed.

The questionnaires will be distributed to fill in at the site, but if too burdensome, the option to complete at home will be given.

If questionnaires for Baseline visit and/or for Day 16 visit was supplied for finalization at home prior to the visit, these are to be collected and reviewed for quality reasons.

The option to distribute questionnaires to fill in prior to next visit will be given, and the forms will be supplied.

A PK sample will be taken for compliance purposes.

5.2.6. Visit - Day 45

Remaining IMP as well as empty blisters and bottles, and patient diary are collected, if not done at Visit at Day 16.

 Version No:

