6.5. Withdrawal criteria

Subjects can discontinue their participation in the study at any time without any consequence to his/her continued treatment. The investigator/sponsor can at any time terminate the study for a subject due to, e.g., unacceptable adverse events/adverse reactions or because the subject does not follow procedures in the study protocol. If the subject discontinues the study, follow-up of this subject will be performed according to the clinic's routine.

7. Study treatments

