8.6.3. Reporting and registration of Adverse Events

At each study visit, adverse events (AE) are registered, starting at intake of first dose of investigational product up to 28 days following the last dose of study drug. All AE that occurs during the study and which are observed by the investigator/study nurse or reported

 Version No:

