	6	Completely gone
20.	In the past year,	have you been constipated?
	1	Yes
	2	No (if you marked No, please skip to question 24)
21.	How frequently a	are you constipated?
	1	Rarely
	2	Occasionally
	3	Frequently times per month
	4	Constantly
22.	How severe are	these episodes of constipation?
	1	Mild
	2	Moderate
	3	Severe

23. Is your co	nstipati	on aettina:		
•	1	Much worse		
	2	Somewhat wors	se	
	3	Staying the sam		
	4	Somewhat bette		
	5	Much better	5 1	
	6	Completely gon	e	
·		Completely gon		
24. In the pas	st vear.	have vou ever lo	st control of vo	our bladder function?
•	1	Never	,	
	2	Occasionally		
	3	•		times per month
	4	Constantly	· · · · · · · · · · · · · · · · · · ·	
25. In the pas	st year,	have you had dif	fficulty passing	urine?
•	1 .	Never	,, ,	
	2	Occasionally		
;	3	Frequently		times per month
	4	Constantly		·
		,		
26. In the pas	st year,	have you had tro	ouble complete	ly emptying your bladder?
	1	Never		
	2	Occasionally		
	3	Frequently		times per month
•	4	Constantly		·
		·		
27. In the pas	st year,	without sunglass	ses or tinted gla	asses, has bright light
bothered you	r eyes?			
	1	Never (if you ma	arked Never, p	lease skip to question 29)
	2	Occasionally		
;	3	Frequently		
•	4	Constantly		
		•		
28. How seve	ere is thi	is sensitivity to b	right light?	
	1	Mild		
	2	Moderate		
;	3	Severe		
29. In the pas	st year,	have you had tro		
	1		arked Never, p	lease skip to question 31)
	2	Occasionally		
;	3	Frequently		
•	4	Constantly		
			_	
		is focusing probl	em?	
	1	Mild		
	2	Moderate		
;	3	Severe		

- 31. Is the most troublesome symptom with your eyes (i.e. sensitivity to bright light or trouble focusing) getting:
 - I have not had any of these symptoms 1
 - 2 Much worse
 - Somewhat worse
 - 4 Staying about the same
 - 5 6 7 Somewhat better
 - Much better
 - Completely gone

Dagbok för studiedeltagare	Studiekod: KI-PROLIFIC-2023	Version 1, 26 Jan 2023
Patientnummer:		

DAGBOK FÖR DELTAGANDE I PROLIFIC POST-AKUT COVID SYNDROM STUDIEN

Fyll i (kryssa) varje gång du tar studiemedicin. Du ska ta morgon och kväll med 12 timmars mellanrum. Skulle du glömma att en dos och det har gått mer än 8 timmar så ska du inte ta den glömda dosen utan du väntar till nästa schemalagda dos. Om du inte tar medicinen vid någon/några tillfällen ange det i kommentarrutan nedan.

Spara alla tablettkartor och burkar, tomma eller med överbliven medicin, och ta med dem på besöket dag 16. Ta även med denna dagbok då och lämna till studiepersonalen.

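### The Safety Analysis Set leaves out anyone who took exactly one dose, and the protocol gives two different end dates for adverse event collection

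*Protocol*

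**What the plan says.** **Safety set.** Section 10.2 defines the Safety Analysis Set as "All participants randomly assigned to study intervention and who take at least 2 doses of study intervention", analysed by the intervention received. It is the only set named for safety and the only one stated to be analysed as received. Section 10.3 promises AE descriptives by treatment group and visit but does not say on which set.

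**Start of AE collection.** Three places agree on the first dose: section 5.2.4 ("Adverse event reporting starts from intake of the first dose of investigational product"), the footnote to Table 1, and section 8.6.3.

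**End of AE collection.** The footnote to Table 1 in section 5.2.1 says "AE's are reported from first intake of study treatment until Day 90 visit", and Table 1 marks adverse events at Day 45 and Day 90. Section 8.6.3 has AEs registered "starting at intake of first dose of investigational product up to 28 days following the last dose of study drug". The sentence after that one covers "All AE that occurs during the study and which are observed by the investigator/study nurse or reported" by the subject, with no 28-day limit.

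**SAEs.** The same footnote has SAEs reported from signed consent to the Day 90 visit. The part of 8.6.3 on reporting SAEs to the manufacturer refers back to an active reporting period defined earlier, and the 28-day wording is the text that precedes it.

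**The concern.** **Safety set.** A safety population should be fixed by exposure. Here a second dose is also required, and whether it is taken can depend on how the first was tolerated. The study diary sets the doses half a day apart ("Du ska ta morgon och kväll med 12 timmars mellanrum"), so there is an interval in which someone can react and stop. The protocol's own text makes this possible: section 3 notes that "ritonavir may cause adverse effects such as nausea", and ritonavir is given in both arms. Section 6.5 lets the investigator or sponsor "terminate the study for a subject due to, e.g., unacceptable adverse events/adverse reactions". After early termination of treatment, assessments are meant to continue to Day 90 where possible (section 5.2.8). A one-dose participant could therefore be followed for three months and still be missing from the safety set.

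**Collection window.** Two current instructions give different end dates. If staff follow the shorter one, later AEs are never recorded, and no analysis plan can recover them. The protocol extends treatment to 15 days while citing safety data for up to 10 days (sections 2.3 and 7.3), so complete collection matters here.

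**Working it through.** The protocol states no figure that can be reproduced for this point. The check compares the texts, does the day arithmetic, and bounds the effect under a stated assumption.

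**Inputs from the protocol**
- 400 randomised 2:1 (section 5.1): about 267 on nirmatrelvir/ritonavir and 133 on placebo/ritonavir.
- Twice daily for 15 days (section 5.1): 15 × 2 = 30 planned doses, the last on Day 15.
- Visit windows: Day 45 ± 7 (Days 38–52) and Day 90 ± 7 (Days 83–97) (Table 1).
- A dose is one intake: section 10.2 counts 25 dosings for other sets, and the diary records morning and evening intakes separately. Exactly one dose is therefore below the threshold of 2.

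**Assumption.** The share stopping after exactly one dose is not given. I take 0–2% of 400, that is 0–8 participants, all with the same AE.

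**Effect on an AE rate.** Let *k* one-dose stoppers in an arm of *n* all have the AE, and let *p* be its rate among the rest.
- Rate in all exposed: [*k* + *p*(*n* − *k*)]/*n*
- Rate in the defined set: *p*
- Understatement: (*k*/*n*)(1 − *p*), largest at *p* = 0

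| 8 stoppers, *p* = 0 | Nirmatrelvir/ritonavir | Placebo/ritonavir |
|---|---|---|
| Split 2:1 | 5.33/267 = 2.0 points | 2.67/133 = 2.0 points |
| All on nirmatrelvir/ritonavir | 8/267 = 3.0 points | 0 |
| All on placebo/ritonavir | 0 | 8/133 = 6.0 points |

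With no such stoppers every entry is 0.

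**AE window**

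| | 28-day limit | Gap to Day 45 visit | Gap to Day 90 visit |
|---|---|---|---|
| Completer, last dose Day 15 | 15 + 28 = Day 43 | 45 − 43 = 2 days (0–9) | 90 − 43 = 47 days (40–54) |
| One dose on Day 1 | 1 + 28 = Day 29 | 45 − 29 = 16 days (9–23) | 90 − 29 = 61 days (54–68) |

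Ranges use the visit windows, for example 83 − 43 = 40 and 97 − 43 = 54. For a completer the disputed period is 47/90 = 52% of the nominal 90 days.

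**The case against.** **No analysis is tied to the set, and the effect may be nil.** Section 10.3 names no set for the AE summaries, so harm requires both that they use this set and that someone stops after exactly one dose. eCRF registration, SAE reporting and safety committee review do not depend on the set. All of this is true and limits the size. It does not rescue the definition: the protocol has fixed the rule, so an analysis plan must either inherit it or contradict it.

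**The upper bounds are stacked.** They need every stopper to have the same AE and nobody else to have it. For a common event such as nausea *p* is above 0 and the effect is smaller. Ritonavir is given at the same dose in both arms, so nausea from it would point to the 2:1 split. Both arms then lose the same share and, at equal AE rates, the difference between arms does not move. This stands. The 3.0 and 6.0 figures are outer limits, not expectations.

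**Section 6.5 only permits early stopping.** No clinic assessment is scheduled between Day −1 and Day 16, so a stop within about 12 hours of the first dose would usually be the participant's own. That is fair: the section shows such stops are possible, not that they are expected.

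**Most of the text supports Day 90.** The Table 1 footnote, the Table 1 marks and the next sentence of 8.6.3 all do, so AEs are lost only if staff follow the one clause that differs. The 52% is calendar time, all of it more than 28 days after a completer's last dose, and not half of the safety information. This stands too, but 8.6.3 is the section staff consult on AE registration, and the clause there is explicit.

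**Conclusion.** Both points hold as matters of wording, and they are separate defects.

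1. The two-dose threshold makes the safety set depend on events after exposure and can understate a reaction that causes immediate stopping. The size is unknown. Under the assumed 0–2% it is 0 to 2.0 points per arm with a 2:1 split, at most 3.0 or 6.0 points if all stoppers are in one arm, and nil if nobody stops after one dose. It applies wherever the Safety Analysis Set is used.
2. The end of AE collection is contradictory by 47 days for a completer (40–54) and by 61 days (54–68) after a single dose on Day 1. The 28-day clause in 8.6.3 is the one out of line with the rest of the protocol.
3. The cross-reference in the SAE text of 8.6.3 needs clarification only, since the Table 1 footnote already gives the SAE period.

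Confidence is high in the wording defects. The likely effect on reported rates is probably modest. The change should be made.

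**What to change.** - **Section 10.2:** define the Safety Analysis Set as all randomised participants who take at least one dose of study intervention, analysed as received.
- **Section 8.6.3 and the Table 1 footnote:** reconcile them to one stated end of AE collection. Collection to the Day 90 visit is already scheduled in Table 1.
- **Section 8.6.3, SAE reporting to the manufacturer:** replace the back-reference with the SAE reporting period written out.

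The cost is a few lines of wording and possibly a few more participants in the safety denominator. No visits are added.

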10.3. Descriptive

Descriptive statistics for all efficacy and safety (AE related variables) endpoints by treatment group and visit will be provided.

The number of participants screened will be reported. The number of participants randomized to the double-blind treatment phase, completing the study drug administration, completing the study, and discontinued the study will be summarized from the FAS analysis set for each treatment group.

Baseline demographic and other characteristics will be tabulated for the FAS analysis set and summarized by treatment group. Continuous variables will be described by standard descriptive statistics (mean, standard deviation, median, interquartile range, minimum, and maximum), and categorical variables will be summarized by frequency tables with number and proportion in each category (with the corresponding sample sizes).

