8.5. Safety assessments

8.5.1. Laboratory safety assessments

Hematology, biochemistry, coagulation, and other analyses will be analyzed at the Hospital Laboratory at Karolinska University Hospital, Solna. The timepoints are summarized in Table 1, Schedule of assessments. The hospital regularly reviews reference values for each of the biomarkers and the reference values are provided by the hospital lab upon delivering lab results. The reference values serve as guidance for the clinician and study team, who will judge whether a value outside of the reference value is clinically significant or not.

Hematology	Chemistry	Other
Hemoglobin	BUN or urea	Ferritin
Hematocrit	Creatinine or Cystatin-C to	Procalcitonin
RBC count	enable eGFR calculation	
Platelet count	using CKD-Epi or CKD-	Haptoglobin
WBC count	EpiCysC	
Total neutrophils (Abs)	Glucose	Thyroid function
Eosinophils (Abs)	Calcium	TSH
Monocytes (Abs)	Sodium	T4 (free)
Basophils (Abs)	Potassium	
Lymphocytes (Abs)	Chloride	Coagulation
	Total CO₂ (bicarbonate)	PT/aPTT
	AST, ALT	Fibrinogen
	Total bilirubin	D-dimer
	Albumin	
	Total protein	HIV test
	NT-proBNP	Pregnancy test (βhCG)¹
	LDH	
	hsCRP	
	ESR	

¹ A negative urine or serum (β-hCG) pregnancy test must be confirmed at screening for WOCBP only. Pregnancy tests will also be done whenever 1 menstrual cycle is missed during the active treatment period (or when potential pregnancy is otherwise suspected) and at Day 15 or ET visit.

The rapid antigen test will be evaluated directly at the clinic after testing.

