8.6. Adverse Events

8.6.1. Definitions

Adverse Event (AE): Any untoward medical occurrence in a clinical investigation subject administered a medicinal product and, which does not necessarily have a causal relationship with the treatment, can be an unfavorable and unintended sign (including an abnormal laboratory discovery), symptom or disease temporally associated with the use of the medicinal (investigational) product, whether related to the medicinal (investigational) product or not.

Serious adverse event (SAE): Any untoward medical occurrence that at any dose:

- results in death
- is life-threatening
- requires inpatient hospitalization or prolongation of existing hospitalization
- results in persistent or significant disability or incapacity
- results in a congenital anomaly/malformation

Medical and scientific assessment will be made to determine if an event is "serious" and whether it would prompt reporting in other situations, for example important medical events that may not be directly life-threatening or result in death or hospitalization but may compromise the study subject or may require intervention to prevent one of the other results set forth in the definitions above. These should also normally be considered as SAEs.

Suspected Unexpected Serious Adverse Reaction (SUSAR)

A SUSAR is a reaction/event that is unexpected, serious, and suspected to be caused by the treatment, i.e., adverse events that are not included in the Investigator's Brochure (IB) or SPC.

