 2.0 Final

 Date:
 10 March 2023

 EudraCT No:
 2022-003855-32

by the subject will be registered in the eCRF regardless of whether they are related to the investigational product or not. Assessment of causal relationship, severity, and whether the AE is considered to be an SAE or not will be done by the investigator directly in eCRF. At minimum, for each AE/SAE, a description of the event is recorded (diagnosis/symptom if diagnosis is missing), start and stop dates, causal relationship, severity, if the AE is considered to be an SAE or not, measures and outcome.

Reporting of Adverse Events (AE)

All AEs shall be registered in the eCRF within 3 working days.

Reporting of Serious Adverse Events (SAE) to Pfizer

Serious adverse events (SAE) are reported to Pfizer, in a protected email with copy to sponsor, on a designated SAE form within 24 hours from when the information received.

For life-threatening events or death, submit the SAE form immediately.

Follow-up information describing the outcome and handling of the SAE is reported as soon as this information is available and not later than 24 hours from when the information is received. The original should be kept in the Investigator Site File.

In addition, SAEs that occur after completion of the active reporting time period as defined above are reportable to Pfizer if the investigator suspects a causal relationship between the Pfizer product and the SAE.

Reporting of potential cases of Drug-Induced Liver Injury (DILI), Assessed Based on Hy's Law criteria

For investigational (non-authorized) medicinal products that are investigational in the United States (irrespective of being authorized elsewhere), interventional clinical study reports with elevations in aspartate aminotransferase (AST) and/or alanine aminotransferase (ALT) in addition to and/or preceding total bilirubin (TBili) elevations (>2 x ULN) are considered potential DILI- (assessed per Hy's law criteria) cases and should always be considered important medical events, even before all other possible causes of liver injury have been excluded.

The threshold of laboratory abnormalities for a potential DILI case depends on the subject's individual baseline values and underlying conditions. Subjects who present with the following laboratory abnormalities should be evaluated further as potential DILI (Hy's law) cases to definitively determine the etiology of the abnormal laboratory values:

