10.4. Statistical methods

For the primary estimand of the primary endpoint, a linear mixed model (LMM) with subject-specific random intercept will be specified to assess possibles changes over time within and among groups. LMM accounts for both fixed and random effects, can analyze data with repeated measures as well as can handle missing values. Specifically, the LMM will include treatment, time, and time*treatment interaction term as fixed effects, and subject/participant as a random effect. An unstructured correlation matrix will be used. Missing values will be imputed as part of the LMM model assumptions.

No adjustments will be made for multiplicity.

For continuous variables, differences in mean or median between groups will be assessed using Student's t-test (parametric) or Mann-Whitney test (non-parametric) depending on the

 Version No:

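### Section 10.3 restricts the by-arm safety summaries to AE-related variables, which is narrower than the safety assessments in 8.5 and leaves the Day 16 liver and kidney results without a named summary

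*Protocol*

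**What the plan says.** Section 10.3 sets the scope of the summaries: "Descriptive statistics for all efficacy and safety (AE related variables) endpoints by treatment group and visit will be provided". The words in parentheses state which safety endpoints are meant.

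Section 8.5 is wider. Under the safety heading it lists laboratory tests (8.5.1), vital signs (8.5.2) and physical examination (8.5.3). The laboratory table includes AST, ALT, total bilirubin, urea, and "Creatinine or Cystatin-C to" allow an eGFR to be calculated. All of these are run centrally: "Hematology, biochemistry, coagulation, and other analyses will be analyzed at the Hospital Laboratory at Karolinska University Hospital, Solna".

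Table 1 schedules the laboratory panel at Screening, Baseline and Days 16, 45 and 90. Footnote k then makes the last two panels conditional on the results of the preceding one: "Laboratory tests at Days 45 and 90 are required only if clinically relevant abnormal laboratory values were present from a sample drawn at the previous". The Early Termination column has no laboratory mark.

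Reference ranges are only a guide for the clinician and study team, "who will judge whether a value outside of the reference value is clinically significant or not" (8.5.1). The AE definition in 8.6.1 admits laboratory findings: an AE "can be an unfavorable and unintended sign (including an abnormal laboratory discovery), symptom or disease temporally associated with the use of the medicinal" product. Section 8.6.3 adds the Hy's law rule for individual cases, with SAE reporting.

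**The concern.** The protocol treats liver and kidney safety as something to watch. Exclusion 16 concerns AST, ALT and bilirubin, exclusion 2 sets an eGFR limit, and 8.6.3 has a full section on drug-induced liver injury, whose cases "should always be considered important medical events, even before all other possible causes of liver injury have been excluded". Yet the sentence that decides which safety data are summarised by arm leaves out the laboratory values themselves.

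Two routes to the results remain. A clinician may judge a value significant and record it as an AE, or AST/ALT and bilirubin may together meet the Hy's law rule. A moderate rise in enzymes in one arm, with normal bilirubin and no AE entry, passes through neither.

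The stake is the safety evidence for this regimen. Treatment lasts 15 days, while sections 2.3 and 7.3 cite safety data up to 10 days. The randomised comparison of Day 16 laboratory values is the trial's main controlled laboratory evidence on the longer exposure.

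**Working it through.** No figure in the plan needs to be reproduced here, because the point rests on the text. An illustration with assumed inputs follows.

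**1. Which safety assessments have a named by-arm summary**

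| Assessment in 8.5 | Named in section 10.3, or an efficacy endpoint in 4.2? |
|---|---|
| AEs | Yes, 10.3 |
| D-dimer, CRP, ESR, ferritin, NT-proBNP, LD | Yes, as secondary endpoints |
| Body temperature | Yes, as a secondary endpoint |
| AST, ALT, total bilirubin | No |
| Creatinine or cystatin-C (eGFR), urea | No |
| Blood pressure, respiratory rate | No |

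So the analytes that bear most directly on liver and kidney safety are among those left out.

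**2. When everyone is measured**

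Baseline and Day 16 are unconditional. At Days 45 and 90 the panel is required only after a clinically relevant abnormality, so those values come from a selected group. Day 16 is the only post-dose visit at which the arms can be compared without that selection. It covers those who attend; the Early Termination visit schedules no panel.

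**3. What the remaining routes capture**

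- AE route: requires a judgement of clinical significance. Exclusion 16 applies to a known history of AST or ALT at or above 2.5 x ULN, so a participant may enter with moderately raised enzymes, and a later isolated rise may be judged unremarkable.
- Hy's law route: with normal baseline values, it requires AST or ALT >3 x ULN and bilirubin >2 x ULN together. It yields individual SAE reports, not a comparison of arms.
- Section 10.4: for continuous variables, "differences in mean or median between groups will be assessed using" a t-test or Mann-Whitney test, chosen by a normality check. For categorical variables it gives a chi-squared or Fisher test. Neither rule excludes laboratory values, and neither names them.

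**4. Illustration (all rates assumed; none is in the protocol)**

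Arm sizes: 400 x 2/3 = 267 active and 400 x 1/3 = 133 control. ALT is taken as log-normal with median 0.6 x ULN and log-SD 0.45 in both arms. A fraction p of the active arm is instead drawn uniformly from 3-6 x ULN. Expected cases = 267 x p. Tests are two-sided at 0.05, with 4,000 simulated trials per row.

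| p | Expected active cases >3 x ULN | Mann-Whitney rejects | t-test rejects | Fisher on counts >3 x ULN rejects |
|---|---|---|---|---|
| 2% | 5.3 | 6% | 17% | 9% |
| 3% | 8.0 | 8% | 35% | 41% |
| 5% | 13.4 | 13% | 76% | 92% |

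Controls above 3 x ULN average about 0.02 per trial. At p = 3% the difference in medians is about 0.01 x ULN. A single table of 8/267 v 0/133 gives a Fisher p of about 0.056.

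If only the planned minimum of 207 completers had a Day 16 panel, the active arm would be 207 x 2/3 = 138. The 3% case would then give 138 x 0.03 = about 4 patients.

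The gain from a count table is therefore mainly that the cases become visible by arm. A formal test may not reach significance at low rates.

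**The case against.** The strongest reply is that section 10 calls itself an outline and leaves further detail to a SAP that is not at hand. Counts by ULN category, shift tables and plots are normal SAP content, so their absence from the protocol is no fault. That stands, and they are not part of the finding. What the reply does not remove is the scope stated in 10.3. A SAP that details this sentence faithfully inherits its restriction.

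A reader might infer that laboratory values have no analysis at all, or that an arm difference would certainly go unreported. The documents do not support either. An abnormal laboratory finding can be an AE (8.6.1). Section 10.4 has general rules for continuous and categorical variables. The Safety Monitoring Committee reviews unblinded data (8.7), and the interim analysis looks at observed safety (10.6). Laboratory tests are repeated after a clinically relevant abnormality. These are real safeguards, but none of them names a by-arm laboratory table for the final results.

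A reader might also infer a known liver harm. The protocol does not say so. Section 2.3 describes adverse events as similar to placebo in earlier trials, and the liver-injury text in 8.6.3 is framed generally. Both arms also receive ritonavir, so the assumption that the whole excess falls in the active arm is only illustrative. Finally, nothing in the documents suggests that clinicians would routinely dismiss values of 3-6 x ULN. The more plausible loss is of smaller shifts.

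**Conclusion.** The point holds as a scope that is stated too narrowly. Section 10.3 defines the safety endpoints for summary as AE-related, while 8.5 treats laboratory tests, vital signs and physical examination as safety assessments. AST, ALT, total bilirubin and creatinine or cystatin-C therefore have no named by-arm summary. A difference that is not judged clinically significant and does not meet Hy's law could go unreported.

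The size cannot be derived from the documents. The simulated figures depend wholly on assumed rates and show only that a mean or rank comparison may hide a rise confined to a few percent of patients. The conclusion does not rest on them. It rests on the wording of 10.3, the content of 8.5, footnote k of Table 1, and 15 days of dosing against cited safety data of up to 10 days. It does assume that the SAP keeps to the scope in 10.3. If the SAP already summarises laboratory values and vital signs by arm, only the protocol wording needs to be reconciled. The change is worth making, and nothing in it affects the primary analysis.

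**What to change.** In 10.3, replace the parenthesis after the word safety with: AEs, laboratory values and vital signs. Add that these are summarised by arm on the Safety Analysis Set defined in 10.2, with Day 16 as the main laboratory time point because later panels are conditional. State that liver tests are also shown as counts by category of the ULN, using the categorical rule already in 10.4. Leave the cut-points, shift tables and plots to the SAP, and check that the SAP uses the same scope.

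The cost is a changed sentence or two and a few standard tables from data already scheduled for collection. It needs no new visit or sample and changes no rule of clinical management.
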